Our study addresses a critical need for real-world interventions that can function in CMHCs and psychiatry clinics to address these medically underserved communities. If successful, this will result in a model that has potential to be disseminated to other under-resourced CMHC settings. This study will test an intervention that has the potential to make improvements in tobacco treatment and ultimately reduce cancer in the SMI patients. For this trial we will recruit broadly at Washington University Psychiatry Clinics. These clinics predominately serve SMI patients.

2. Objectives

Aim 1: test the effect of nudges to quit on patient receipt of tobacco treatment. The investigators hypothesize patient receipt of tobacco cessation treatment such as medication and counseling will be higher after delivery of nudges to quit over usual care.

Aim 2, the investigators will test the effect of nudges to quit on smoking behaviors. The investigators hypothesize that smoking behaviors will decrease and quitting behaviors will increase in the nudges to quit group compared to usual care.

Aim 3, the investigators will evaluate the feasibility and preliminary effect of this pilot project for a future R01 proposal to systematically evaluate this multilevel intervention adapted for CMHCs and psychiatry clinics.

3. Participant selection

3.1 Eligibility Criteria

Inclusion Criteria:

1. Patient of participating clinic
2. Current smoker, ≥ 5 cigarettes per day
3. Age 18 years or older
4. Can speak and understand English

Exclusion Criteria:

1. Active use or receipt of smoking cessation medication or smoking cessation counseling (within the past 30 days)

3.2 Inclusion of women and minorities

Women and members of all races and ethnic groups are eligible for this study.

4. Recruitment and informed consent

Research team members plan to recruit, consent, and enroll patients of the participating clinics into the study.

4.1 Recruitment

A study team member will identify patients who are potentially eligible via Epic or patient list provided by clinic and will:

1. Mail the individual a letter and/or flyer inviting the individual to participate in the study. A phone number and email address will be provided for the individual to indicate interest in the study to the study team.
2. Call the potential participant. A study team member will use a verbal script to describe the study, and address any questions the potential participant may have.
3. Send an invitation via MyChart to participants, if applicable.
4. Patients will be recruited by fliers posted in the clinic (with clinic prior approval).

If participants are interested in the study they will be screened for eligibility using a script and a research team member will collect eligibility information and consent as approved by IRB.

4.2 Informed Consent

Participants will have the opportunity to give consent verbally over the phone without documentation of signature or in person with documentation of signature at a study location outside of the clinic. If consent is attained over the phone, the study team member will review the consent, obtain verbal consent, and mail a copy to the participant. If consent is attained in person, a research member will review the paper information consent. We will ask the patient to indicate participation by signed consent form. There will be an opportunity for the participant to ask the research team questions and the study team will document assent, including questions asked, using the consent documentation instrument in REDcap. The research team member who discusses the consent with the participant will document the conversation. After any questions are addressed

and the consent is complete, a copy of the consent will be delivered to the participant. To reduce the possibility for coercion, participants will have as much time as they desire to consider enrolling in the study including the opportunity to thoroughly review the consent materials with knowledgeable members of the research team, and with family and/or friends as appropriate and sufficient time to have all questions answered.

5. Registration procedures

This study will register summary accrual statistics to the Siteman Cancer Center OnCore Database. On a quarterly basis, accrual should be grouped according to the demographic data collected. Demographic information includes gender, age, ethnicity, and race. If any piece of demographic information was not collected for those categories, choose unknown.

1. In OnCore, navigate to the PC Console for this study and enter the dates of the quarter for which you are entering accrual statistics. (These dates must be inclusive of the same year, e.g. 1/1/2020 – 3/31/2020, not 12/31/2019 – 3/31/2020.)
2. Then, enter the accrual number for any subjects who are in the same demographic groups of race, ethnicity, gender, and age group. For example, if you have accrued two white non-Hispanic males in their 50s, you will enter that demographic as an accrual group of 2. If you have also accrued an Asian female in her 40s, you will enter her as a separate accrual group (you would enter “1” for the accrual number.)
3. In addition, you will enter “Research Center” in the drop-down field for “Internal Accruing Reporting Group” and “No disease” in the drop-down field for “Disease Site.”

Complete instructions can be accessed in the OnCore Users’ Manual:

<https://cbmiapps.wustl.edu/confluence/display/OSS/6.+Summary+Accruals>

6. Methods

6.1 Study overview

The overarching goal of this pilot project is to reduce the disparity in the treatment of tobacco use among patients at psychiatry clinics with low burden, multi-level implementation strategies, a important need reflected in existing evidence and a recent survey of community needs. The investigators propose a pilot randomized trial of 60 patients. Patients will be randomized with 1:1 allocation to usual care vs. intervention “Nudges to Quit”.

TRIAL OVERVIEW	Recruit, Screen, Consent	Baseline	Follow Up	Follow Up
Timeline	Prior to baseline	Day 0	Month 3	Month 6
Location	Phone	Zoom/ Phone/ Study Lab	Zoom/ Phone/ Study Lab	Zoom/ Phone/ Study Lab
Remuneration	-	\$50	\$50	\$50
COMMUNICATIONS				

Mail Recruitment Letters/ Call to recruit/ Flyers	X			
ADMINISTRATIVE				
Screening/ Eligibility Check	X	X		
Informed Consent	X	X		
Contact Information		X		
ASSESSMENTS AND DATA				
Demographics		X		
Smoking History/Status		X	X	X
Smoking Treatment History and Interest		X	X	X
Bioverified point prevalence abstinence (patients reporting abstinence)			X	
Use of Nicotine and Tobacco		X	X	X
FTND		X	X	X
WSWS		X	X	X
Credibility, Acceptability and Expectancy		X	X	X
Readiness to Quit		X	X	X

FTND= Fagerström Test for Nicotine Dependence, WSWS= Wisconsin Smoking Withdrawal Scale; NTQ - Nudges to Quit; UC- usual care

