6.3 Enrollment

Patients will be randomized after completion of baseline assessment to either usual care or “nudges to quit”. Once randomization occurs, the participant will be considered enrolled.

6.4 Intervention:

Nudges to Quit-

a. Patient:

- i. Content: Patients will receive a basic handout (example attached) for patient education on evidence-based Guideline-recommended tobacco treatment and a nudge report based on patient reported treatment needs (example attached).
- ii. *Delivery methods:*
 - a. *Mailed and Email Delivery:* A patient handout and patient nudge to quit mailed and/or emailed (password protected with pin number, if emailed) to participants.
 - b. *Verbal Delivery:* A study team member will deliver the patient nudge with a brief coaching interaction based on the public health service guidelines and 5A's approach.
- iii. *Timing:* We will deliver the intervention report on the day of or <=7 days of the baseline visit. A booster intervention report will be mailed and/or emailed in 1 month following the baseline visit.

b. *Provider :*

- i. Content: Providers will receive a nudge report (example attached) based on patient reported treatment needs. For example, providers will receive a nudge message informing them of their patients' cigarettes smoked per day, interest in medication and free smoking cessation programs, and guidance on what they can do to help their patient. Attached to the message will be a triage card that encourages providers to give advice and refer. Triage cards will also correspond to patient interest profiles.
- ii. *Delivery Methods:* The providers of the participants will be sent via secure email and/or inbasket message.
- iii. *Timing:* We will deliver the intervention report on the day of or <=7 days of the baseline visit. A booster intervention report will be mailed and/or emailed in ~1 month following the baseline visit.

Usual Care:

- a. *Patient:*
 - i. Content: Patients will receive a basic handout (example attached) for patient education on evidence-based Guideline-recommended tobacco treatment.
 - ii. *Delivery Methods:*
 - a. *1. Mailed and Email Delivery:* A patient handout and patient nudge to quit will be mailed and/or emailed (password protected with pin number, if emailed) to participants.
 - b. *Verbal Delivery:* A study team member will deliver the patient nudge with a brief coaching interaction based on the public health service guidelines and 5A's approach.

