Aim 1 analysis: We will compare the patient receipt of tobacco treatment for smoking cessation during at 6 months visit across the 2 arms. This pilot trial will be limited in statistical power due to its small sample size, but will provide important estimates for R01 proposal power calculations.

Aim 2, the investigators will test the effect of nudges to quit on smoking behaviors.

The investigators hypothesize that smoking behaviors will decrease and quitting behaviors will increase in the nudges to quit group compared to usual care. This pilot trial will be limited in statistical power due to its small sample size, but will provide important estimates for R01 proposal power calculations.

Aim 3, the investigators will evaluate the feasibility and preliminary effect of this pilot project for a future R01 proposal to systematically evaluate this multilevel intervention adapted for CMHCs. These data will inform the design of a future larger well powered trial to evaluate the multilevel intervention rigorously. Participant perspectives on acceptability of the intervention, collected during follow up visits, will be used to motivate this future work.

This is a pilot trial to evaluate feasibility and preliminary effects. No statistical tests will be pursued.

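### Baseline treatment interest is recorded before randomization, but neither the 1:1 allocation nor the Aim 1 comparison uses it: a modest, avoidable loss of precision

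*Combined protocol and SAP*

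**What the plan says.** Section 6.1 gives the size, "The investigators propose a pilot randomized trial of 60 patients", and the allocation, "Patients will be randomized with 1:1 allocation to usual care vs. intervention". Section 6.3 adds the timing: "Patients will be randomized after completion of baseline assessment". The public text names no sequence method, blocks, strata, minimization or concealment.

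The assessment table in Section 6.1 marks "Smoking Treatment History and Interest" at baseline, month 3 and month 6, so each patient's interest is on file when the arm is assigned. Section 6.4 uses it in the intervention. Among the examples of what the provider message reports is "interest in medication and free smoking cessation programs, and guidance on what they can do to help their patient", and it adds: "Triage cards will also correspond to patient interest profiles".

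The Aim 1 analysis in Section 9 reads: "We will compare the patient receipt of tobacco treatment for smoking cessation during at 6 months visit across the 2 arms". It names no covariate, stratum, effect measure or interval. Section 9 also says that no tests will be run and that the estimates are meant for the power calculations of a later grant application.

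**The concern.** With about 30 patients per arm, chance can leave one arm with clearly more patients who already want treatment. If such patients are more likely to obtain it, that arm will show more receipt whether or not the nudge works. Section 3.1 excludes anyone with cessation medication or counseling in the past 30 days, so everyone starts untreated. A recent baseline value of the outcome therefore cannot do the correcting, and a baseline predictor would have to.

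The stake is the quality of one number. No test is planned, so no type I error rate is at issue, but the Aim 1 estimate is to inform the size of a larger trial. Any noise that a baseline item could have removed goes into that design.

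**Working it through.** **Inputs from the documents.** Total 60, allocation 1:1, hence nominally 30 per arm before dropout (Section 6.1). The plan states no alpha, power, effect size or receipt rate, so it has no figure of its own to reproduce.

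**Assumed inputs, not in the documents.** Share interested q; receipt a in interested and b = 10% in other patients; no treatment effect.

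**1. How often a gap of 20 points arises, q = 50%, 30:30.** Twenty points is 6 patients of 30.
- If each patient is independently interested with probability 50%, the number interested in one arm plus the number not interested in the other is Binomial(60, 0.5). A gap of 6 or more means at most 24 or at least 36: probability 0.155.
- If exactly 30 of the 60 are interested, the count in one arm is hypergeometric. A gap of 6 or more means at most 12 or at least 18: probability 0.196.

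Hence about 15% to 20%. The two figures differ only in what is held fixed.

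**2. What a 20-point gap does to the estimate.** Shift = gap × (a − b). At receipt of 40% and 10%: 0.20 × 0.30 = 0.06, or 6 points with no treatment effect.

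**3. What using interest gains.** With p = qa + (1 − q)b, the variance of the raw risk difference is 2p(1 − p)/30. Balance on interest removes the between-group part, so the proportional reduction is q(1 − q)(a − b)² / [p(1 − p)].

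| q | a / b | p | Reduction in variance |
|---|---|---|---|
| 50% | 40% / 10% | 0.25 | 0.0225 / 0.1875 = 12% |
| 50% | 30% / 10% | 0.20 | 0.0100 / 0.1600 = 6% |
| 50% | 20% / 10% | 0.15 | 0.0025 / 0.1275 = 2% |
| 80% | 40% / 10% | 0.34 | 0.0144 / 0.2244 = 6% |
| 80% | 30% / 10% | 0.26 | 0.0064 / 0.1924 = 3% |
| 80% | 20% / 10% | 0.18 | 0.0016 / 0.1476 = 1% |
| 90% | 40% / 10% | 0.37 | 0.0081 / 0.2331 = 3% |
| 90% | 30% / 10% | 0.28 | 0.0036 / 0.2016 = 2% |
| 90% | 20% / 10% | 0.19 | 0.0009 / 0.1539 = 0.6% |
| 40% | 50% / 10% | 0.26 | 0.0384 / 0.1924 = 20% |
| any | a = b | – | 0% |

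**4. In standard errors, first row.** Raw: √(2 × 0.1875/30) = 0.112. Balanced: √(2 × 0.1650/30) = 0.105. The 95% half-width falls from 1.96 × 0.112 = 0.22 to 1.96 × 0.105 = 0.206.

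**5. Stratified analysis without stratified allocation.** Simulating the first row with unstratified 30:30 allocation and a Mantel-Haenszel risk difference gives a variance ratio of about 0.90, against 0.88 under exact balance. Most of the gain therefore comes from the analysis alone.

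**The case against.** The strongest case against is one of weight. Chance imbalance after randomization is variance, and an unadjusted confidence interval already allows for it. In the 50%, 40%/10% scenario the half-width shrinks only from about 22 to 20.6 points, which would hardly change how a pilot without tests is read. Patients volunteer in response to letters, calls and flyers (Section 4.1), so interest may be common and the gain smaller still. Readiness to quit, nicotine dependence and treatment history are also collected at baseline, so interest is not the only candidate. All of this stands, and it is why the point is minor. The reply is that Section 9 plans no interval, so nothing would show that uncertainty, and that the remedy costs almost nothing.

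A reader might infer three stronger things that the documents do not support.
- That the Aim 1 contrast is biased by the allocation. Unstratified randomization is not biased.
- That the protocol treats interest as decisive for receipt. Section 6.4 tailors messages to it, and lists it among examples; that does not show that it predicts receipt.
- That arm sizes will be unequal. A simple coin toss would give 24:36 or worse with probability 0.155, but no section says that one will be used. Even that split raises the variance by only about 4%: (1/24 + 1/36)/(2/30) = 1.042.

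**Conclusion.** The point holds as a minor loss of precision. Allocation is stated only as 1:1, and the Aim 1 comparison names no adjustment, although a plausible predictor of receipt is in hand at randomization. For 50% to 90% interested and receipt of 20% to 40% against 10%, the variance saving is about 2% to 12% in most combinations, and 1% or less where interest is very common and weakly predictive. It reaches about 20% with 40% interested and receipt of 50% against 10%, and is nil if interest does not predict receipt. All these rates are assumptions, and 30 per arm is the number before dropout. Part of the file was removed before review, so the absence of an allocation method is a statement about the public text.

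A separate and larger problem affects the same contrast. Aim 1 is read at 6 months, after usual-care patients are due to receive the nudge at 3 months (Sections 6.2 and 6.4). Using baseline interest does nothing about that.

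**What to change.** In Section 9, report the Aim 1 risk difference stratified by baseline treatment interest (interested in medication or counseling: yes or no), with Mantel-Haenszel weights and a confidence interval, next to the raw proportions by arm. This works even if enrollment has closed.

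If allocation is still open, state in Sections 6.1 and 6.3 that it uses concealed permuted blocks of varying size, stratified by the same yes/no item.

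Cost: one or two sentences in Section 9 and, if adopted, an allocation list with two strata. The interest questions must be reduced to one yes/no rule, fixed in advance. For stratified allocation the item must also be scored before the arm is assigned, which the order of procedures already permits. The expected gain is modest.

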6.2 Patient participation

Patients who participate will be asked to complete 3 assessments either over the phone, in person on paper or via secure redcap questionnaire administered by a research team member. Patients will be asked to complete a pre-appointment tobacco treatment needs assessment (baseline). This assessment will collect demographic, smoking, and treatment information about the patient (see trial overview table), and in part will be used as decision support for their provider via nudge creation. If patients are randomized to nudges to quit their provider will receive the nudge within one week post pre-appointment tobacco treatment needs assessment. At three month and three six months, the study team will assess tobacco treatment and smoking behaviors such as readiness to quit, smoking abstinence, smoking quantity, and quit attempts. If patients are randomized to usual care, the provider will receive the nudge following three month assessment.

These assessments will occur at study visits outside of regular clinic visits.

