6.6 Retrospective EHR query

De-identified EHR data will be queried, as approved by IRB. We will examine patient smoking prevalence, diagnosis codes, and proportion receiving tobacco treatment (medication and counseling) from EHR data. Data will be provided as approved by the Washington University Institutional review board.

7. Risks and Benefits

Participants may or may not benefit from being in this study. However, we hope that, in the future, other people might benefit from this study because knowledge generated from this research could advance the delivery of smoking cessation treatment.

Participation in this study does not entail any risks that are greater than those ordinarily encountered in daily life. It is possible that a participant will feel uncomfortable during the assessment. If that is the case, they can refuse to answer that particular question or discontinue the assessment altogether.

There is a risk of breach of confidentiality. All reasonable steps will be taken to ensure that patient privacy is maintained.

8. Regulatory and reporting requirements

We expect that the occurrence of a serious adverse event as it relates to these study interventions to be extremely rare. If a breach of confidentiality were to occur, it would be reported to QASMC and HRPO within 10 days of notification.

This study does not require QASMC audit or submission of DSM reports. In case of severe adverse events requiring immediate attention the study team will have a call schedule to ensure an on-call clinician and a back-up clinician are always available for the study team for safety assessment. If both the on-call clinician and back up clinician cannot be reached, the staff will recommend the participant to contact their existing primary care doctor or psychiatrist or go to the emergency room for evaluation and refer the participant to crisis hotline or other community resources that may be beneficial to the participant.

9. Statistical Considerations

Aim 1: test the effect of nudges to quit on patient receipt of tobacco treatment.

The investigators hypothesize patient receipt of tobacco cessation treatment such as medication and counseling will be higher after delivery of nudges to quit over usual care.

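### Receipt of treatment is collected by the team that delivers the coaching, with no masking or role separation described and no EHR check linked to arm, so Aim 1 is exposed to differential self-report, most clearly at month 3

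*Combined protocol and SAP*

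**What the plan says.** All references are to the combined protocol and SAP.

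- **Who collects the outcomes.** Section 6.2 offers phone, paper in person, or a questionnaire "via secure redcap questionnaire administered by a research team member". At months 3 and 6, "the study team will assess tobacco treatment and smoking behaviors such as readiness to quit, smoking abstinence, smoking quantity, and quit attempts".
- **Who delivers the intervention.** Section 6.4, on the spoken route: "A study team member will deliver the patient nudge with a brief coaching interaction based on the public health service guidelines and 5A's approach". NTQ patients are due this within 7 days of baseline. Usual-care (UC) patients are due it on the day of the 3-month visit or within 7 days of it.
- **What measures treatment.** The schedule in section 6.1 lists "Smoking Treatment History and Interest" at baseline, month 3 and month 6. It is the only scheduled item on treatment.
- **What is verified.** The same schedule has "Bioverified point prevalence abstinence (patients reporting abstinence") at month 3 only.
- **What the records could add.** Section 6.6: "De-identified EHR data will be queried, as approved by IRB". Its content includes the "proportion receiving tobacco treatment (medication and counseling) from EHR data". Neither trial participants nor arms are mentioned.
- **What is analyzed.** Section 9 compares receipt of treatment between arms at the 6-month visit and names no data source. Section 6.4 says outcomes are assessed at 3 months, after which UC patients receive the NTQ intervention.

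The documents do not mention masking of assessors or separation of the coaching and assessing roles.

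**The concern.** Receipt of treatment, cigarettes per day, quit attempts and readiness all appear to come from what the patient tells the study team. The coaching encourages patients to take up treatment and to quit. A patient who has been coached by that team has some reason to tell the team that the advice was followed. A patient who has not been coached has less reason. Up to month 3 this contrast coincides with the randomized contrast, so over-reporting would look like an effect of the nudge on Aim 1 and on the self-reported part of Aim 2.

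Two features of the plan could limit this, and neither does so for Aim 1 as written. Bioverification checks abstinence, not whether medication or counseling was received. The EHR query covers exactly the Aim 1 construct, but no route from it to the randomized comparison is described.

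No tests are planned, so the estimate itself is the product: section 9 says that it will feed the R01 power calculations. An interval shows sampling error but does not show a directional reporting error.

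**Working it through.** The plan gives no treatment rate, effect size or over-reporting rate, so there is no figure of its own to reproduce.

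**Inputs from the documents.** 60 patients at 1:1 (section 6.1) give 60 / 2 = 30 per arm.

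**Assumed inputs.** True receipt p is the same in both arms. A share f of untreated patients in an arm wrongly report treatment.

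**Step 1: spurious difference.** With no true effect, the observed difference is (1 − p) × (f in NTQ − f in UC).

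**Step 2: month 3.** Set f = 0 in UC, the case most favorable to a bias, and p = 20%:
- f = 5%: 0.80 × 0.05 = 4 points
- f = 10%: 0.80 × 0.10 = 8 points (28% observed against 20%, or 2.4 extra patients of 30)
- f = 15%: 0.80 × 0.15 = 12 points

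For p from 10% to 30% and f from 5% to 20%, the range is 0.70 × 0.05 = 3.5 points to 0.90 × 0.20 = 18 points, or about 1 to 5 extra patients of 30.

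**Step 3: comparison with sampling error.** The 95% half-width is 1.96 × √(2p(1 − p)/30). It is 15 points at p = 10%, 20 points at p = 20% and 23 points at p = 30%. The 4 to 12 points at p = 20% lie inside it. Only the extreme corner (p = 10%, f = 20%, 18 points) exceeds its own half-width.

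**Step 4: month 6.** UC patients are by then also due the coaching, and more recently, so f in UC need not be zero. At p = 20%, f of 10% in NTQ and 5% in UC gives 0.80 × 0.05 = +4 points. Reversed, it gives −4 points. The sign is not determined.

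**Step 5: what it could do to R01 planning.** Suppose true receipt is 20% against 30% and f = 10% in NTQ only. Observed NTQ receipt is 0.30 + 0.70 × 0.10 = 37%. Patients per arm for 80% power at two-sided 5% are (1.96 + 0.8416)² × [p₁(1 − p₁) + p₂(1 − p₂)] / (p₂ − p₁)²:
- observed, 20% vs 37%: 7.849 × (0.16 + 0.2331) / 0.0289 ≈ 107
- true, 20% vs 30%: 7.849 × (0.16 + 0.21) / 0.01 ≈ 291

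With 107 per arm, the standard error for the true rates is √(0.37 / 107) = 0.0588. Power is Φ(0.10 / 0.0588 − 1.96) = Φ(−0.26), about 40%, if the later trial measures receipt without this error.

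**The case against.** Several stronger readings are tempting, and the documents do not support them.

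- **That one unblinded person both coaches and assesses.** Sections 6.2 and 6.4 show a shared team, not a shared individual, and are silent on masking. Staff at a month-3 visit may need to know who is UC in order to deliver the delayed nudge, but that is an inference.
- **That the EHR data cannot be split by arm.** De-identified data can carry an arm code if they are linked before identifiers are removed. What can be said is that no linkage or arm-level analysis is described. The retrospective query may never have been meant as a trial outcome.
- **That Aim 1 is biased toward the hypothesis.** The mechanism needs coaching in one arm only. Section 9 places the Aim 1 comparison at 6 months, when UC patients are due the same coaching. This is the strongest objection, and it stands: a direction is supported at month 3 only.
- **That the EHR is free of bias.** NTQ providers receive a nudge and a triage card, so charting may itself differ by arm.

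Other limits also stand. Verbal delivery is qualified as being where applicable, so the number of NTQ patients coached is unknown. Patients know whether they were coached, so a masked interviewer removes only part of the problem. Bioverified abstinence at month 3 is an objective check on part of Aim 2. The over-reporting rates are assumed and one-sided, the plan concedes low power, and it plans no tests.

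These points lower the grade of the concern without removing it. Section 9 still offers the estimate for later power calculations, and the plan describes no independent check on receipt of treatment by arm.

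**Conclusion.** The concern holds as a risk of differential self-report, not as a demonstrated bias. It rests on what the plan leaves undescribed: assessor masking, separation of coach from assessor, linkage of EHR treatment data to participants or arm, and the Aim 1 data source. The risk is sharpest at month 3. At month 6 its direction is unclear.

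The size is unknown. The 4 to 12 points depend on 20% true receipt in both arms, accurate UC reporting, and over-reporting by 5% to 15% of untreated NTQ patients. An error of that size is smaller than the pilot's sampling error, so it would not dominate the pilot's own reading, but it would be carried unseen into the R01 estimate. This is a worthwhile low-cost improvement, not a flaw that invalidates the pilot.

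**What to change.** 1. **Section 6.6.** For the 60 randomized participants, extract cessation medication orders and counseling referrals by study ID, without reference to arm. Do so from baseline to month 3 and, separately, from month 3 to month 6. Report them by arm beside self-report, and note that the nudge may also affect provider charting. Keep the wider clinic query de-identified.
2. **Section 6.2.** Have the follow-up treatment and smoking items self-completed on paper or in REDCap where possible. Otherwise, have them asked by an existing team member who did not coach that participant and is not shown the arm. Complete the month-3 assessment before any delayed UC nudge is delivered, since section 6.4 allows both on the same day.
3. **Sections 6.4 and 9.** Reconcile the 3-month and 6-month outcome time points, name the data source for Aim 1, and match the main EHR window to the time point chosen.

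**Cost.** An IRB amendment, any consent needed for linkage (the consent pages are not in the reviewed text, so this cannot be judged here), modest extraction work for 60 records, and some reassignment of tasks. Item 2 assumes that the team is large enough to separate the roles. EHR data miss over-the-counter products and quitline use, so they supplement self-report and do not replace it.
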